**Table 5. Summary of Efficacy Variables and Corresponding Analyses for Long-Term Efficacy Analysis**

Efficacy Variables	Analysis Method
Binary Endpoints:	

 
• ACR20/50/70 response by visit
 
• LDA and CR based on DAS28(CRP), DAS28 (ESR), SDAI, and CDAI criteria by visit
 
• Proportion of subjects with change from baseline in HAQ-DI <math>\leq -0.3</math> and <math>\leq -0.22</math>, respectively
 
• Boolean remission
 
• Proportion of subjects with no concomitant corticosteroid use (among subjects with corticosteroid use at baseline)*
 
	
 
• Point estimate and 95% CI of the response rate for each randomized treatment group sequence
 
• Point estimate and 95% CI of the response rate using GLMM model for each randomized treatment group sequence (*endpoint excluded from this analysis)
 
• Plot for each randomized treatment group sequence over time for key endpoints#
 
• Imputation: AO
 
• Analysis Set: FAS
 

Continuous Endpoints:	

 
• Change from baseline in individual ACR components by visit
 
• Change from baseline in DAS28 (CRP) and DAS28 (ESR) by visit
 
• Change from baseline in CDAI and SDAI by visit
 
• Change from baseline in morning stiffness (severity and duration) by visit
 
• Change from baseline in EQ-5D-5L by visit
 
• Change from baseline in FACIT-F
 
• Change from baseline in RA-WIS
 
• Change from baseline in SF-36 by visit
 
	
 
• Point estimate and 95% CI of mean change from baseline together with SD, for each randomized treatment group sequence
 
• Point estimate and 95% CI of change from baseline using MMRM model for each randomized treatment group sequence
 
• Plot for each randomized treatment group sequence over time for key endpoints#
 
• Imputation: AO
 
• Analysis Set: FAS
 

# Key endpoints for figures include: ACR20/50/70, LDA and CR based on DAS28(CRP) and CDAI criteria, Boolean remission, change from baseline in DAS28(CRP) and CDAI.

## 9.4 Efficacy Variables Definitions and Conventions

### 9.4.1 ACR Criteria

ACR criteria are a commonly used standard criteria set mentioned in the guidance of American College of Rheumatology to evaluate the effectiveness of investigation drug in

RA clinical trials. It is a composite measurement calculated based on the improvement over a set of core measurements.

ACR20 is defined as at least 20% improvement (compared to baseline values) in tender and swollen joint counts and at least 20% improvement in 3 of the remaining 5 core set measures (subject global assessment of pain, subject global assessment of disease activity, physician global assessment of disease activity, subject assessment of physical function and acute phase reactant hsCRP).

ACR50 and ACR70 are similarly defined with at least 50% and 70% improvement, respectively.

A subject will be classified as an ACR20 (ACR50, ACR70) responder, if the following conditions are met:

1.  $\geq 20\%$  (50%, 70%) improvement from baseline in tender joint count (TJC68) and
2.  $\geq 20\%$  (50%, 70%) improvement from baseline in swollen joint count (SJC66) and
3.  $\geq 20\%$  (50%, 70%) improvement from baseline in at least 3 of the following 5:
  - patient's assessment of pain
  - patient's global assessment of disease activity (PGA)
  - physician's global assessment of disease activity (PhGA)
  - patient's self-assessment of physical function (i.e., measured by Health Assessment Questionnaire (HAQ-DI score))
  - Acute-phase reactant value CRP

There are seven components to be evaluated to define an ACR response. Missing values for each component can occur due to a missed visit or due to dropout from the study. Depending on the pattern of the missing components, ACR responses may be or may not be determined using observed values only.

To maximize the utilization of observed information at certain visits and be scientifically as robust as possible, the principle to calculate ACR response is to minimize imputation whenever possible. Observed ACR response will be calculated first based on a derived visit window instead of the nominal visit identifier (e.g., Week 6 visit) collected from the CRF.

To calculate observed ACR responses:

- 1 means achieving  $\geq$  xx% improvement from baseline and 0 means  $<$  xx% improvement from baseline (e.g., xx% representing 20%/50%/70%).
- ACRxx = 0 if TJC indicator = 0 OR SJC indicator = 0 OR at least 3 out of 5 components improvement indicators = 0.
- ACRxx = 1 if TJC indicator = 1 AND SJC indicator = 1 AND at least 3 out of 5 components improvement indicators = 1.
- For all other cases, ACRxx = missing since ACRxx cannot be determined.

The following table illustrates examples for ACR calculations.

Example	TJC 68	SJC 66	Component 1	Component 2	Component 3	Component 4	Component 5	ACR20-Response?
A	1	1	1	1	1	.	.	Yes
B	1	0	1	1	1	1	1	No
C	.	0	.	.	.	.	.	No
D	1	.	1	1	1	1	1	.
E	1	1	0	0	0	1	1	No
F	.	.	0	0	0	.	.	No
G	1	1	1	1	0	0	.	.

Legend: 1 =  $\geq$  20% improved compared to baseline; 0 =  $<$  20% improved compared to baseline; "." missing

Windowing Rule for ACR Response Calculation:

- ACR component values will first be determined at each date within a visit window.

- ACR component values at each date will be combined to determine the observed ACR composite score at each date in each window.
- After this calculation, if multiple non-missing ACR composite scores are available within a given visit window, the non-missing ACR composite score closest to the target day will be used. If two composite scores have the same distance from the target day, the later one will be used. The corresponding date will be used as the observed ACR response date in the derived efficacy dataset.
- If a non-missing ACR composite score is not available for any day within a given visit window, the windowed component values for that visit will be used to calculate the ACR composite score for that visit window (component value windowing follow the same rules as in steps described above). The date of observed ACR composite score will be determined by the first available ACR component date, in the order of TJC, SJC, Pain, PGA, PhGA, HAQ-DI, CRP/ESR, in the derived efficacy dataset.

When observed ACR xx response for a given visit is missing, imputation methods will be used to calculate "imputed" ACRxx response.

Non-Responder Imputation (NRI) for ACR response:

- Step 1: all missing components will be imputed using LOCF, and then the ACR composite score can be calculated.
- Step 2: if the ACR composite score cannot be determined by Step 1, the ACR composite score will be imputed as 0. In addition, subjects who prematurely discontinue from the study drug will be considered as nonresponders (ACR = 0) for all subsequent visits after the discontinuation date.

#### **9.4.2 Joint Evaluation**

Anatomical joints are evaluated for swelling and tenderness at every study visit. The 34 anatomical joints in [Table 6](#) are assessed in this study for both the left and right side of the body.

**Table 6. Anatomical Joints Assessed for Calculation of Tender and Swollen Joint Counts (TJC68 and SJC66)**

Temporomandibular	Sternoclavicular	Acromio-Clavicular	Shoulder
Elbow	Wrist	Metacarpophalangeal I	Metacarpophalangeal II
Metacarpophalangeal III	Metacarpophalangeal IV	Metacarpophalangeal V	Thumb Interphalangeal
Proximal Interphalangeal II	Proximal Interphalangeal III	Proximal Interphalangeal IV	Proximal Interphalangeal V
Distal Interphalangeal II	Distal Interphalangeal III	Distal Interphalangeal IV	Distal Interphalangeal V
Hip a	Knee	Ankle	Tarsus
Metatarsophalangeal I	Metatarsophalangeal II	Metatarsophalangeal III	Metatarsophalangeal IV
Metatarsophalangeal V	Great Toe/Hallux	Interphalangeal II	Interphalangeal III
Interphalangeal IV	Interphalangeal V		

a. Hip joints are not assessed for swelling.

At each study visit, a joint evaluator assessed whether a particular joint was "tender or painful" where presence of tenderness was scored as "1" and the absence of tenderness was scored as "0," provided the joint was not replaced ("9") or could not be assessed ("NA") due to other reasons (e.g., post-corticosteroid joint injection). The total tender joint count (TJC68), which is based on 68 joints, will be derived as the sum of all "1s" and proportional extrapolation will be used to impute joint counts for the joints that are replaced or not assessed. A similar method will be followed for the derivation of total swollen joint count (SJC66), which is based on 66 joints as the hip joints are excluded. Thus, the range for TJC68 will be 0 to 68 and 0 to 66 for SJC66.

### **9.4.3 Patient's Global Assessment of Disease Activity Visual Analog Scale (VAS)**

The subject will assess his/her disease activity for the past 24 hours using a Patient's Global Assessment of Disease VAS. The range is 0 to 100 mm with no activity being indicated by 0 and severe activity by 100.

#### **9.4.4 Physician's Global Assessment of Disease Activity Visual Analog Scale (VAS)**

The physician will assess Patient's disease activity at the time of visit using a Physician's Global Assessment of Disease VAS. The range is 0 to 100 mm with no activity being indicated by 0 and severe activity by 100.

#### **9.4.5 Patient's Global Assessment of Pain**

The subject will assess his/her pain in the previous week using a Patient's Global Assessment Pain VAS. The range is 0 to 100 mm with no pain being indicated by 0 and severe pain by 100.

#### **9.4.6 Disease Activity Score (DAS28)**

DAS28 (CRP) and DAS28 (ESR) are composite indices to assess disease activity in RA patients using hsCRP or ESR measurement respectively. The DAS provides a score between 0 and 10, indicating how active the rheumatoid arthritis is at the time of measurement.

DAS28 (CRP) and DAS28 (ESR) can be calculated based on Tender Joint Count, Swollen Joint Count, Patient's Global Assessment of Disease Activity (PtGA) (in mm), and hsCRP (in mg/L) or ESR (mm/hr).

$$\text{DAS28 (CRP)} = 0.56 \times \sqrt{\text{TJC28}^*} + 0.28 \times \sqrt{\text{SJC28}^{**}} + 0.36 \times \ln(\text{hsCRP}\& + 1) + 0.014 \times \text{PtGA}\gg + 0.96$$

$$\text{DAS28 (ESR)} = 0.56 \times \sqrt{\text{TJC28}^*} + 0.28 \times \sqrt{\text{SJC28}^{**}} + 0.70 \times \ln(\text{ESR}\#) + 0.014 \times \text{PtGA}\gg$$

\* TJC28 refers to the Subject's total Tender Joint Count out of the provided 28 evaluated joints.

\*\* SJC28 refers to the Subject's total Swollen Joint Count out of the provided 28 evaluated joints.

& hsCRP refers to the high-sensitivity c-reactive protein lab value. hsCRP unit in the DAS28 (CRP) equation is expressed as mg/L.

# ESR refers to the Erythrocyte sedimentation rate. ESR unit in the DAS28 (ESR) equation is expressed as mm/hr.

» PtGA refers to the Patient's Global Assessment of Disease Activity.

where  $\sqrt{\phantom{x}}$  is square root and  $\ln$  is natural log.

**Table 7. Anatomical Joints for DAS28(CRP) Calculation**

Shoulder	Elbow	Wrist	Thumb Interphalangeal
Metacarpophalangeal I	Metacarpophalangeal II	Metacarpophalangeal III	Metacarpophalangeal IV
Metacarpophalangeal V	Proximal Interphalangeal II	Proximal Interphalangeal III	Proximal Interphalangeal IV
Proximal Interphalangeal V	Knee		

To calculate observed DAS28 scores, the observed component value will be calculated first. Then the components will be included in the calculation per the DAS formula selected. If any observed component is missing in a window, then the observed DAS28 score will be missing.

#### **9.4.7 Simplified Disease Activity Index (SDAI)**

SDAI is a composite continuous index to assess disease activity based on TJC28, SJC28, Patient's Global Assessment of Disease Activity (PtGA) (in cm, 0 – 10), Physician's Global Assessment of Disease Activity (PhGA) (in cm, 0 – 10) and hsCRP (mg/dL). It can be derived as follows:

$$SDAI = TJC28 + SJC28 + PtGA (cm) + PhGA (cm) + hsCRP (mg/dL).$$

To calculate observed SDAI scores, the observed component value will be calculated first. Then the components will be included in the calculation per the SDAI formula selected. If any observed component is missing in a window, then the observed SDAI score will be missing.

#### **9.4.8 Clinical Disease Activity Index (CDAI)**

CDAI is a composite continuous index to assess disease activity without using hsCRP measurement. It can be calculated based on TJC28, SJC28, Patient's Global Assessment of Disease Activity (PtGA) (in cm, 0 – 10) and Physician's Global Assessment of Disease Activity (PhGA) (in cm, 0 – 10). It can be derived as follows:

$CDAI = TJC28 + SJC28 + PtGA (cm) + PhGA (cm).$

To calculate observed CDAI scores, the observed component value will be calculated first. Then the components will be included in the calculation per the CDAI formula selected. If any observed component is missing in a window, then the observed CDAI score will be missing.

#### 9.4.9 Clinical Remission (CR) and Low Disease Activity (LDA)

Clinical remission (CR) and low disease activity (LDA) based on DAS28 (CRP), DAS28(ESR), SDAI and CDAI are defined as follows:

	DAS28 (CRP) and DAS28 (ESR)	SDAI	CDAI
LDA	$\leq 3.2$	$\leq 11.0$	$\leq 10$
CR	$< 2.6$	$\leq 3.3$	$\leq 2.8$

#### 9.4.10 ACR/EULAR Boolean Remission

ACR/EULAR Boolean remission is defined based on the following four criteria:

- Tender joint count  $\leq 1$  (based on 28 joints)
- Swollen joint count  $\leq 1$  (based on 28 joints)
- CRP  $\leq 1$  mg/dL
- Patient global assessment of disease activity  $\leq 10$  (mm)

All four criteria must be satisfied at a visit for a subject to be classified as achieving ACR/EULAR Boolean remission.

#### 9.4.11 Disability Index of Health Assessment Questionnaire (HAQ-DI)

HAQ-DI is a self-reported patient outcome measurement. It is calculated as the mean of the scores from 8 following categories with a range 0 – 3: Dressing and Grooming,

Rising, Eating, Walking, Hygiene, Reach, Grip, and Activities. The higher the score, the more likely to associate with morbidity and mortality for the RA patient.

The maximum score for all the questions in each category is considered as the score for the category. The Standard disability index (HAQ-DI) takes into account the subject's use of aids or devices or assistance in the scoring algorithm for a disability category. For each of the eight disability categories there is an AIDS OR DEVICES companion variable(s) that is used to record the type of assistance, if any, a subject uses for his/her usual activities. If aids or devices and/or assistance from another person are checked for a disability category, the score for this category is set to 2 (much difficulty), if the original score is 0 (no difficulty) or 1 (some difficulty). The HAQ-DI is then calculated by summing the adjusted categories scores and dividing by the number of categories answered. The HAQ-DI cannot be calculated if the patient does not have scores for at least 6 categories.

#### **9.4.12 EuroQoL-5D (EQ-5D-5L)**

EQ-5D is a standardized measure of health status developed by the EuroQol Group in order to provide a simple, generic measure of health for clinical and economic appraisal. The EQ-5D consists of 2 pages. The first page measures 5 dimensions of the health status (mobility, self-care, usual activities, pain/discomfort, and anxiety/depression) with 5 levels per dimension (no problems, slight problems, moderate problems, severe problems, and extreme problems corresponding to Level 1 to Level 5 respectively). The second page is an EQ Visual Analogue Scale (EQ VAS). EQ-5D health states, defined by the EQ-5D-5L descriptive system on the first page, may be converted into a single index value. The change from baseline of the index value and EQ VAS will be analyzed and reported. UK scoring algorithm will be used.

#### **9.4.13 Form SF-36v2**

The 36-Item Short Form, Version 2 (SF-36v2) Questionnaire with 4 week recall will be completed by the subject at Baseline, Weeks 4 and at study completion (Week 12 or at PD). The SF-36v2 health survey consists of 36 general health questions and this study is

using the form for 4 weeks recall period (standard form). It has 2 components: physical and mental. For each component, a transformed summary score is calculated using 8 sub-domains: physical functioning, role-physical, bodily pain, general health, vitality, social functioning, role-emotional, and mental health.

The coding and scoring for the SF-36 will use the software provided by Quality Metrics.

#### **9.4.14 Functional Assessment of Chronic Illness Therapy-Fatigue (FACIT-F)**

Fatigue is one of the most frequent complaints of the elderly and is strongly associated with loss of independence and decreased physical activity and functional decline. One validated tool to measure fatigue is FACIT Fatigue Scale v4. The FACIT Fatigue Scale is a short, 13-item, easy to administer tool that measures an individual's level of fatigue during their usual daily activities over the past week. Each of the fatigue and impact of fatigue items are measured on a four point Likert scale. The FACIT Fatigue Scale is ranged from 0 to 52 and the higher the score, the better the quality of life.

Score for each item is calculated by either subtracted from 4 or adding 0 depending on whether it is a reversal item or not. FACIT Fatigue Scale is then calculated by adding up all item scores, multiplied by 13 and divided by the number of items answered. It is essentially a prorated subscale if there are missing values for some items. If less than or equal to 50% of the items are answered (e.g., 6 out of 13), the proration is not acceptable and the scale will not be computed.

#### **9.4.15 Work Instability Scale for Rheumatoid Arthritis (RA-WIS)**

The 23-item RA-WIS is a simple validated tool to evaluate work instability (the consequence of a mismatch between an individual's functional ability and their work tasks). It can be self-administered by the patients. To calculate the RA-WIS scale, one can simply add up the number of "true" responses. If the scale is < 10, it means low risk and no action is needed. If the scale is between 10 and 17, it means medium risk and

appropriate advice and information should be given. If the scale is > 17, it means high risk and it could warrant referral.

## **10.0 Safety Analysis**

### **10.1 General Considerations**

Safety analyses will be carried out using the Safety Analysis Set. There are two sets of planned safety analysis: safety analysis for Period 1, and long-term safety analysis.

#### **Safety Analysis for Period 1**

Standard safety analysis by the "as treated" treatment groups of Upadacitinib 15 mg QD, Upadacitinib 30 mg QD, and combined placebo groups will be performed on safety data in Period 1. No protocol-defined treatment switching will occur prior to the end of Period 1.

The standard safety analyses will include reporting of adverse events (AEs), laboratory, and vital signs measurements. Frequency tables of subjects with treatment-emergent adverse events (TEAEs) by system organ class (SOC) and by preferred term (PT) as in the Medical Dictionary for Regulatory Activities (MedDRA) dictionary will be provided by treatment group. Mean changes from baseline in all continuous laboratory parameters and vital signs variables at each visit will be summarized by "as treated" treatment group. Frequency tables of subjects meeting criteria for potentially clinically significant vital sign values and for potentially clinically significant laboratory values will be provided by treatment group. Missing safety data will not be imputed.

#### **Long-Term Safety Analysis**

Long-term safety analyses that account for protocol-defined treatment switching include reporting of AE rate adjusted by cumulative exposure, mean change from baseline in laboratory parameters and vital sign variables, and rate of potentially clinically significant laboratory and vital signs values. The treatment-emergent adverse event (TEAE) rate per 100 patient-years of exposure will be presented by actual treatment received at the time of

AE (as described in Section 10.2.2). Listing of subjects with TEAEs by SOC and PT will be provided. Mean changes from baseline in all continuous laboratory parameters and vital signs variables at each visit will be summarized by "as treated" treatment group sequences defined as follows (as described in Section 10.3.3 and Section 10.4.3). Frequency tables and listings of subjects meeting criteria for potentially clinically significant vital sign values and for potentially clinically significant laboratory values will be provided by actual treatment received at the time of event. Missing safety data will not be imputed.

"As treated" treatment group sequences:

1. Upadacitinib 15 mg QD
2. Upadacitinib 30 mg QD
3. Placebo → Upadacitinib 15 mg QD
4. Placebo → Upadacitinib 30 mg QD

Starting with Amendment 6, all subjects will receive open-label upadacitinib 15 mg QD, including those currently on upadacitinib 30 mg QD. For subjects who previously received upadacitinib 30 mg QD, adverse events and exposure to upadacitinib 30 mg QD will be censored at the time of dose switch; subsequent adverse events and exposure starting the day of first dose of upadacitinib 15 mg QD will be summarized under a separate group, as defined in Section 8.1. Assessment of potentially clinical significant laboratory and vital sign values will be based on the same treatment exposure groups as for adverse events, as described above. For summary of mean change from baseline in laboratory values and vital signs, exposure sequences 2 and 4 (i.e., subjects who switched from upadacitinib 30 mg QD to 15 mg QD) will be censored at the time of dose switch. Mean change from baseline for laboratory values and vital signs collected after dose switch will be summarized separately by visits post switch.

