### **Definition of Analysis Windows**

The following rules will be applied to assign actual subject visits to protocol-specified visits. For each protocol-specified study visit, a target study day will be identified to

represent the corresponding visit along with a window around the target day. Windows will be selected in a non-overlapping fashion so that a collection date does not fall into multiple visit windows. If a subject has two or more actual visits in one visit window, the visit closest to the target day will be used for analysis. If two visits are equidistant from the target day, then the later visit will be used for analysis.

The visit window and the target study day for each protocol-specified visit in Period 1 are displayed in [Table 1](#) and [Table 2](#) (depending on the different visit schedules of different endpoints). Visit windows for protocol-specified visits in Period 2 are defined similarly.

**Table 1. Analysis Windows for Efficacy Analysis for Period 1 (for ACR Components and Morning Stiffness) and Safety Analysis for Period 1 (for Labs and Vital Signs)**

Protocol Specified Visit Week	Lower Bound	Target Day	Upper Bound
Baseline	-99	1 a	1
1	2	8	11
2	12	15	22
4	23	29	43
8	44	57	71
12	72	85	min (99, first dose date of Period 2)

a. Day of first dose of study drug.

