### **Summary of Dose Switch from Upadacitinib 30 mg QD to 15 mg QD**

Starting with Amendment 6, all subjects will receive open-label upadacitinib 15 mg QD, including those currently on upadacitinib 30 mg QD. The visit at which dose switch occurs could be different for each subject. For subjects on upadacitinib 30 mg QD in Period 2, the number and percentage of subjects switching to upadacitinib 15 mg QD at each visit will be summarized.

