## **8.0 Study Drug Exposure and Compliance**

### **8.1 Study Drug Exposure**

The duration of exposure to study drug will be summarized for the safety analysis set by the following groups.

1. Placebo

2. Upadacitinib 15 mg QD

This includes upadacitinib 15 mg QD exposure from subjects starting on upadacitinib 15 mg QD and subjects switching from placebo to upadacitinib 15 mg QD.

3. Upadacitinib 30 mg QD

This includes upadacitinib 30 mg QD exposure from subjects starting on upadacitinib 30 mg QD and subjects switching from placebo to upadacitinib 30 mg QD. Exposure is censored at time of dose switch from upadacitinib 30 mg QD to upadacitinib 15 mg QD.

4. upadacitinib 15 mg QD switched from upadacitinib 30 mg QD

This includes upadacitinib 15 mg QD exposure from subjects who switched dose from upadacitinib 30 mg QD to upadacitinib 15 mg QD.

Starting with Amendment 6, all subjects will receive open-label upadacitinib 15 mg QD, including those currently on upadacitinib 30 mg QD. Exposure to upadacitinib 30 mg QD (Group 3) will be censored prior to the day subject received the first dose of upadacitinib 15 mg QD, and subsequent exposure to upadacitinib 15 mg QD will be summarized under a separate group (Group 4).

The duration of exposure to study drug will be summarized for each group as specified above, with the number of subjects, mean, standard deviation, median, minimum and maximum values. In addition, the number and percentage of subjects exposed to study drug will be summarized for the following cumulative duration intervals.

- $\geq 2$  weeks
- $\geq 1$  month
- $\geq 3$  months
- $\geq 6$  months

- $\geq 9$  months
- $\geq 12$  months
- $\geq 18$  months
- $\geq 2$  years
- $\geq 2.5$  years
- $\geq 3$  years
- $\geq 4$  years

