### **10.3.3.2 Assessment of Potentially Clinical Significant Laboratory Values**

Long-term laboratory data will be summarized based on the number and percentage of subjects meeting the criteria for potentially clinical significant laboratory values and by the actual treatment received at the time of the event occurrence. Starting with Amendment 6, all subjects will receive open-label upadacitinib 15 mg QD, including those currently on upadacitinib 30 QD. The treatment groups for summarizing potentially clinical significant laboratory values are the same as the ones for long-term AE analysis as described in Section 8.1 and Section 10.2.2. A subject can be counted under different treatment groups if he/she switched treatment and experienced potentially clinical significant laboratory values under different treatment groups.

In the evaluation of potentially clinically significant laboratory values, the baseline value will be determined by the last non-missing measurement recorded on or before the date of the first dose of study drug in the corresponding treatment group (which may be different than the first dose of study drug received in the study). For example, for a subject who started on Placebo and switched to upadacitinib 15 mg QD, lab values under upadacitinib 15 mg QD exposure would be evaluated against the baseline value defined as the last non-missing measurement recorded on or before the date of the first dose of upadacitinib 15 mg QD. For subjects who switched from upadacitinib 30 mg QD to upadacitinib 15 mg QD, lab values under upadacitinib 15 mg QD exposure would still be evaluated against the baseline defined based on the first dose of upadacitinib 30 mg QD.

A listing of all subjects with any laboratory determination meeting OMERACT criteria of Grade 3 or 4 will be provided by Grade. For creatine phosphokinase and creatinine, NCI CTC criteria will be used. For each of these subjects, the whole course of the respective parameter will be listed.

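### In the long-term tables of clinically significant laboratory, liver and vital-sign values, a switch-visit value taken before the first 15 mg dose can be counted as a post-switch 15 mg result

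*SAP*

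**What the plan says.** SAP 8.1 defines four exposure groups for long-term safety: placebo (1), 15 mg (2), 30 mg (3), and 15 mg switched from 30 mg (4). These are not the four randomised groups, which carry the same numbers.

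- **Where 30 mg ends.** Group 3 exposure "will be censored prior to the day subject received the first dose of upadacitinib 15 mg QD" (SAP 8.1).
- **Where Group 4 starts.** "subsequent adverse events and exposure starting the day of first dose of upadacitinib 15 mg QD will be summarized under a separate group" (SAP 10.1, Long-Term Safety Analysis).
- **Extension to laboratory values and vital signs.** "Assessment of potentially clinical significant laboratory and vital sign values will be based on the same treatment exposure groups as for adverse events" (SAP 10.1). SAP 10.3.3.2 repeats it: "The treatment groups for summarizing potentially clinical significant laboratory values are the same as the ones for long-term AE analysis". SAP 10.3.3.3 does the same for liver elevations and 10.4.3 for vital signs.
- **A second principle.** The same sections (10.1, 10.3.3.2, 10.3.3.3, 10.4.3) say these values are presented by the treatment the subject was actually receiving when the event occurred.
- **When the switch happens.** "The visit at which dose switch occurs could be different for each subject" (SAP 7.0).
- **Baseline for switchers.** Laboratory values on 15 mg after 30 mg "would still be evaluated against the baseline defined based on the first dose of upadacitinib 30 mg QD" (SAP 10.3.3.2). SAP 10.4.3 does likewise for vital signs.
- **Mean-change summaries.** These have their own rule in SAP 10.1: the 30 mg sequences are cut at the time of the switch, and only values collected after it are shown by post-switch visit.

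**The concern.** The boundary is set by calendar day, and it was written for adverse events and exposure, where a whole day has to go somewhere. A laboratory or vital-sign value is different: it is a point measurement. If it is taken before the first 15 mg dose it describes the subject on 30 mg, whatever the date says.

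The PCS tables count subjects with at least one qualifying value. If a subject has an abnormal value at the switch visit and it resolves on 15 mg, the day rule still shows that subject as a case in the post-switch group. The 30 mg group loses the value. The comparison most likely to be drawn from Groups 3 and 4, whether abnormalities settle after dose reduction, is then tilted against showing recovery.

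**Working it through.** No figure in either document depends on this rule, so there is nothing to reproduce. The check has two parts.

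**1. Can a pre-dose value fall on the first 15 mg date?**

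- Protocol Table 4 schedules central laboratory tests, vital signs and drug dispensing at the same Period 2 visits through Week 240.
- Protocol 5.5.4 keeps the subject's regular dosing time on visit days. A subject who has not yet dosed can be sampled, receive the 15 mg supply and take it that day. The value is then dated on the first 15 mg date, and the day rule puts it in Group 4. A subject who has already taken 30 mg that morning starts 15 mg the next day, and the value stays in Group 3.

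**2. Does anything else in the SAP catch it?**

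- *Placebo to upadacitinib.* Two safeguards apply. The Week 12 window for laboratory tests and vital signs in SAP Table 1 runs to "min (99, first dose date of Period 2"), so the first-dose date stays in Period 1. SAP 10.3.3.2 also lets a value on or before the first-dose date be the new baseline.
- *30 mg to 15 mg.* The baseline is not reset, so the switch-day value remains an ordinary post-baseline value.
- *Clock time.* SAP 10.2 has a time-of-day exception for adverse events on the study drug start date. None is written for laboratory or vital-sign values at the switch.

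**Size (illustration).** The inputs below are assumptions, because the documents give none of them:

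- q = risk of a PCS value per visit, taken as equal on both doses, with visits independent;
- m = number of assessments after the switch;
- f = share of switched subjects whose first 15 mg dose is on the visit day.

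Percentage of subjects with any PCS value in Group 4:

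- correct attribution: 1 − (1 − q)^m
- day rule: 1 − (1 − q)^m × (1 − f·q)

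With q = 1% and m = 4, correct attribution gives 1 − 0.99^4 = 3.94%. Under the day rule:

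| f | Group 4 | Extra subjects per 300 |
|---|---|---|
| 0.25 | 1 − 0.9606 × 0.9975 = 4.18% | 0.7 |
| 0.5 | 1 − 0.9606 × 0.995 = 4.42% | 1.4 |
| 1 | 1 − 0.9606 × 0.99 = 4.90% | 2.9 |

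The 300 is the planned 200 + 100 subjects allocated to 30 mg in Period 2. It is an upper limit, before attrition.

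Over q = 0.5% to 3%, m = 1 to 8 and f = 0.25 to 1, the day rule inflates the Group 4 percentage by a factor of 1.03 to 2.0 and adds 0.4 to 8.7 subjects per 300. The misplaced share of Group 4 assessments is f/(m + f): 0.25/8.25 = 3% at the low end, 1/2 = 50% at the high end.

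Two departures from these assumptions work in opposite directions. Correlation within subjects shrinks the effect: with q = 3%, m = 6 and f = 1, the rise is from 16.7% to 19.2% if visits are independent, but from 12.1% to 13.4% with a latent normal correlation of 0.5. A higher risk on 30 mg enlarges it: with 6% on 30 mg and 3% on 15 mg, independent visits give 1 − 0.97^6 = 16.7% rising to 1 − 0.97^6 × 0.94 = 21.7%.

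**The case against.** The strongest reply is that the SAP already states the right principle. Values go by the treatment actually being received, so a pre-dose sample belongs to 30 mg. On this view, sharing exposure groups with adverse events only names the table columns and is not a timing rule for samples. Table 1 supports this reading, since it keeps a first-dose date in the earlier period and SAP 5.2 says Period 2 windows are defined similarly.

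Part of this stands: the SAP points both ways. But the principle does not cancel the day-level boundary, which is the only operational rule written for this switch. Table 1 sets visit windows, not the switch boundary. A programmer who follows 8.1 and 10.1 literally will place the value in Group 4.

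Other parts of the reply limit the scope, and they stand. A reader might infer any of the following, and the documents do not support them:

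- *That all laboratory and vital-sign summaries are affected.* The mean-change summaries do not use the day-of-dose wording, although they leave the time of the switch undefined.
- *That every switched subject is affected.* Only those assessed on the date of their first 15 mg dose are, and that share is not given.
- *That Group 4 is the only view of laboratory safety after the switch.* Post-switch mean change is summarised separately, and the whole course of the parameter is listed for each subject with a qualifying value, so recovery can be seen there.
- *That 15 mg in general is made to look worse.* The values enter a separately labelled group. The main 15 mg group (Group 2) is untouched.

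**Conclusion.** The point holds for three sets of long-term tables: PCS laboratory values, liver elevations and PCS vital signs. There the day-of-first-dose rule can place a value that reflects 30 mg in Group 4, against the SAP's own principle of attribution by treatment at the time.

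The direction is certain. The number of subjects counted can only stay the same or rise in Group 4, and stay the same or fall in Group 3. At most one visit per switched subject is involved.

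The size is not known. The 3.9% to 4.2–4.9% example rests on an assumed 1% risk, four later visits, independence and equal risk on both doses, so it illustrates scale and does not estimate the bias. Any later assessment lowers the misplaced share, including the 30-day follow-up, where Table 4 also schedules central laboratory tests and vital signs.

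Period 1 and the primary analysis are unaffected. SAP 11.1 says they were completed under version 2.0 and that the current version governs only later long-term reporting.

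**What to change.** State in SAP 10.1, 10.3.3.2, 10.3.3.3 and 10.4.3 that, for the PCS laboratory, liver-elevation and PCS vital-sign tables:

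- a value dated on or before the date of the first 15 mg dose after 30 mg is attributed to Group 3, unless a recorded time shows that it was collected after that dose;
- Group 4 begins with later values.

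Use the same definition of the time of the switch for the mean-change summaries. Leave the boundary for adverse events and exposure as it is.

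The cost is one sentence in each place and a small programming change, with no new data. There is one small drawback: an adverse event and a laboratory value dated on the switch day may fall in different groups (a creatine phosphokinase event in Group 4 and the value itself in Group 3, for instance). A table footnote can explain this.

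Two cross-references can be corrected at the same time. SAP 10.3.3.1 refers to Section 11.1, the change log, for the post-switch summary, and 10.4.3 refers in one place to Section 9.1 for the exposure groups, which are defined in 8.1.
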